7.2.1 Grading and Recording Tachypnea

The Uganda Ministry of Health (MoH) has put forth guidelines for practitioners that indicate a respiratory rate of 20 or more breaths per minute as abnormal, however respiratory rates in Kampala (at an altitude of 3900 feet), while not well defined, have been commonly observed at a rate of 20 breaths per minute (or above) without any underlying or acute illness. Given the higher respiratory rate noted in guidelines and observations, any instances of a respiratory rate that meets the grade 1 criteria in Appendix 6 will not be recorded as an AE unless it is an increase from the participant’s baseline respiratory rate and all instances of gradable respiratory rate will be considered unrelated to the IP in the absence of any evidence of pathology that may indicate otherwise.

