7.0 PHARMACOVIGILANCE, SAFETY, AND ADVERSE EVENT REPORTING

7.1 Definitions

An adverse event (AE) is any untoward medical occurrence in a clinical investigation participant administered a pharmaceutical product and does not necessarily have a causal relationship with this product. An AE can therefore be any unfavorable and unintended sign (including an abnormal laboratory finding), symptom, or disease temporally associated with the use of a medicinal (investigational) product, whether or not related to the medicinal (investigational) product. (International Conference on Harmonization (ICH) E6) (Synonym: Adverse Experience).

A serious adverse event (SAE): An adverse event or suspected adverse reaction is considered "serious" if, in the view of either the investigator or sponsor, it results in any of the following outcomes: Death, a life-threatening adverse event, inpatient hospitalization or prolongation of existing hospitalization, a persistent or significant incapacity or substantial disruption of the ability to conduct normal life functions, or a congenital anomaly/birth defect. Important medical events that may not result in death, be life-threatening, or require hospitalization may be considered serious when, based upon appropriate medical judgment, they may jeopardize the participant and may require medical or surgical intervention to prevent one of the outcomes listed in this definition. Examples of such medical events include allergic bronchospasm requiring intensive treatment in an emergency room or at home, blood dyscrasias or convulsions that do not result in inpatient hospitalization, or the development of drug dependency or drug abuse (21 CFR 312.32).

“Life-threatening” refers to an adverse event that at occurrence represents an immediate risk of death to the participant. An event that may cause death if it occurs in a more severe form is not considered life-threatening. Similarly, a hospital admission for an elective procedure is not considered an SAE.

All AEs will have their possible relationship to study vaccine assessed and will be graded according to the table for grading severity of adverse events (see Appendix 6). Arthralgia (joint pain) and arthritis AEs will be graded in accordance with the criteria in Appendix 7.

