7.5 Criteria for Study Pause or Termination

The PI will closely monitor and analyze study data as they become available and will make determinations regarding the presence and severity of adverse events. The administration of study injections and new enrollments will be paused and the IND Sponsor will be promptly notified according to the following criteria:

- **One** (or more) participant experiences a **SAE** that is assessed as possibly, probably or definitely related to study agent, or
- **Two** (or more) participants experience the same **Grade 3 or 4** adverse event assessed as possibly, probably or definitely related to study agent.

Plan for Review of Pauses and Resuming Rules:

The study injections and enrollments would resume only if review of the adverse events that caused the pause resulted in a recommendation to permit further study injections and study enrollments. The reviews to make this decision will occur as follows:

Pauses for SAEs: The IND Sponsor and PSRT will consult with the SMC to conduct the review and make the decision to resume, amend or close the study for any SAEs that meet the criteria for pausing the study. The FDA will be notified of any SAE pause review.

Pauses for Grade 3 or 4 AEs: The IND Sponsor and PSRT will conduct the review and make the decision to consult the SMC, resume, amend or close the study for the Grade 3 or 4 events that meet the criteria for pausing the study. As part of the pause review, the reviewers will also advise on whether the study needs to be paused again for any subsequent Grade 3 or 4 event of the same type. The FDA will be notified of all Grade 3 or 4 pause reviews.

When indicated, safety data reports and changes in study status (study pauses) will be submitted to the IRB in accordance with institutional policy.

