APPENDIX 6: GRADING SEVERITY OF ADVERSE EVENTS

FDA Guidance for Industry (September 2007): “Toxicity Grading Scale for Healthy Adult and Adolescent Volunteers Enrolled in Preventive Vaccine Clinical Trials”

Modification to the FDA AE Grading Table

Individuals of African descent have lower neutrophil counts than individuals of other ethnicities. A study evaluating the reasons for ineligibility in phase I and II HIV vaccine trials in East Africa found that approximately one third of subjects were excluded because of neutropenia. The phase I and II studies used normal ranges from U.S. populations, not from African populations. If neutrophil ranges from East/South Africa populations were used instead, over one half of the subjects excluded because of hematologic abnormalities could have been included (ref.). Since this study will be conducted in part in East Africa, we will use the normal neutrophil range from East/South Africa ($1.0 - 5.3 \times 10^3$ cells/ul, (ref.) for subjects in Uganda or other subjects of African descent. Grades for absolute neutrophil count in these subjects will be as follows:

	Grade 1	Grade 2	Grade 3	Grade 4
Absolute Neutrophil Count (cells/ul)	750 – 999	500 – 749	250 – 499	< 250

For other subjects, the usual FDA AE grading scale will be used as follows:

	Grade 1	Grade 2	Grade 3	Grade 4
Absolute Neutrophil Count (cells/ul)	–1,500 – 2,000	1,000-1,499	500 - 999	< 500

Assessment of Causality Relationship of an Adverse Event (AE) to Study Vaccine:

The relationship between an AE and the vaccine will be assessed by the investigator on the basis of his or her clinical judgment and the definitions below.

- **Definitely Related.** The AE and administration of study agent are related in time, and a direct association can be demonstrated.
- **Probably Related.** The AE and administration of study agent are reasonably related in time, and the AE is more likely explained by study agent than other causes.
- **Possibly Related.** The AE and administration of study agent are reasonably related in time, but the AE can be explained equally well by causes other than study agent.
- **Not Related.** There is not a reasonable possibility that the AE is related to the study agent.

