Grade 4 (Potentially Life-threatening): Hospitalization; immediate medical intervention or therapy required to prevent death.

Grade 5 (Death): Death is assigned a Grade 5 severity.

Only the single adverse event that is assessed as the primary cause of death should be assigned “grade 5” severity.

**Toxicity Grading Scale for Healthy Adult and Adolescent Volunteers Enrolled in
Preventive Vaccine Clinical Trials
Modified from FDA Guidance - September 2007**

A. Tables for Clinical Abnormalities

Local Reaction to Injectable Product	Mild (Grade 1)	Moderate (Grade 2)	Severe (Grade 3)	Potentially Life Threatening (Grade 4)
Pain	Does not interfere with activity	Repeated use of non-narcotic pain reliever > 24 hours or interferes with activity	Any use of narcotic pain reliever or prevents daily activity	Hospitalization
Tenderness	Mild discomfort to touch	Discomfort with movement	Significant discomfort at rest	Hospitalization
¹ Erythema/Redness	2.5 – 5 cm	5.1 – 10 cm	> 10 cm	Necrosis or exfoliative dermatitis requiring medical attention
² Induration/Swelling	2.5 – 5 cm and does not interfere with activity	5.1 – 10 cm or interferes with activity	> 10 cm or prevents daily activity	Necrosis requiring medical attention
³Vital Signs				
	Mild (Grade 1)	Moderate (Grade 2)	Severe (Grade 3)	Potentially Life Threatening (Grade 4)
⁴ Fever (°C) (°F)	38.0 – 38.4 100.4 – 101.1	38.5 – 38.9 101.2 – 102.0	39.0 – 40 102.1 – 104	> 40 > 104
Tachycardia - beats per minute	101 – 115	116 – 130	> 130	Hospitalization for arrhythmia
⁵ Bradycardia - beats per Minute	50 – 54	45 – 49	< 45	Hospitalization for arrhythmia
Hypertension (systolic) - mm Hg	141 – 150	151 – 155	> 155	Hospitalization for malignant hypertension
Hypertension (diastolic) - mm Hg	91 – 95	96 – 100	> 100	Hospitalization for malignant hypertension
Hypotension (systolic) – mm Hg	85 – 89 and symptomatic	80 – 84 and symptomatic and requiring oral fluids	< 80 and symptomatic and requiring IV fluids	Hospitalization for hypotensive shock
⁶ Respiratory Rate – breaths per minute	17 – 20	21 – 25	> 25	Intubation

1. In addition to grading the measured local reaction at the greatest single diameter, the measurement should be recorded as a continuous variable.
2. Induration/Swelling should be evaluated and graded using the functional scale as well as the actual measurement.
3. Subject should be at rest for all vital sign measurements.
4. Oral temperature; no recent hot or cold beverages or smoking.

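### Section 7.2.1 presets every gradable respiratory rate as unrelated to the vaccine, so isolated Grade 3 tachypnea cannot count toward the pause rule

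*Combined protocol and SAP*

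**What the plan says.** Section 7.2.1 contains two rules with different reach.

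- **Recording.** "any instances of a respiratory rate that meets the grade 1 criteria in Appendix 6 will not be recorded as an AE" unless the rate has risen from the participant's baseline. This rule is limited to Grade 1 and depends on baseline.
- **Attribution.** "all instances of gradable respiratory rate will be considered unrelated to the IP in the absence of any evidence of pathology" that points the other way. This rule has neither limit.

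The reason given is that rates in Kampala, described as not well defined, "have been commonly observed at a rate of 20 breaths per minute (or above) without any underlying or acute illness".

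The Appendix 6 grading row reads "Respiratory Rate – breaths per minute 17 – 20 21 – 25 > 25 Intubation": Grade 1 is 17 to 20, Grade 2 is 21 to 25, Grade 3 is above 25 and Grade 4 is intubation. Footnote 6 to that table already tells the investigator to use judgment from 17 upward and to weigh baseline, local normal values and elevation.

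The general causality rules are elsewhere. Section 7.1: "All AEs will have their possible relationship to study vaccine assessed". Section 7.2 leaves the determination of relationship to the clinical investigators. Appendix 6 says the relationship "will be assessed by the investigator on the basis of his or her clinical judgment", using four defined categories. Section 7.5 pauses the study when two or more participants have the same Grade 3 or 4 "adverse event assessed as possibly, probably or definitely related to study agent", or when one participant has a related serious adverse event. Section 8.3.2 tabulates adverse events by dose level, severity and relationship.

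**The concern.** An attribution fixed before any data exist replaces a judgment that the rest of the protocol asks the investigator to make. A high local norm can explain a high reading at baseline. It does not explain a participant whose rate was unremarkable on Day 0 and above 25 a few days after injection. The same sentence in 7.2.1 treats a rise from baseline as informative when deciding whether to record a Grade 1 value, then ignores it when assigning relationship.

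Safety is the primary objective and there is no control arm, so the relationship column carries much of the information on attribution. The Grade 3 or 4 pause criterion depends directly on that attribution. A preset attribution therefore settles one prespecified safety trigger in advance for this sign.

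**Working it through.** The documents state no figure on this point to reproduce. The check is mainly a comparison of passages, followed by an illustration.

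**1. Scope of the default.** The attribution rule covers every gradable rate, so by the Appendix 6 cut-points it reaches Grades 1, 2 and 3 (17 upward) and, formally, Grade 4.

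**2. Reach of the rationale.** It refers to 20 per minute or above. That plausibly covers part of Grade 2. It states no upper limit, cites no distribution, and says nothing about rates above 25 or about change within a participant.

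**3. Causality standard.** In Appendix 6, Possibly Related needs reasonable timing and applies even when other causes explain the event equally well. Evidence of pathology is not required. Section 7.2.1 requires it, so the bar for this one sign is higher than the protocol's own definition.

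**4. A worked case.** Take two participants with rates below 17 on Day 0 and above 25 at the Day 3 visit, with no other findings.

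| Step | Under 7.1, 7.2 and Appendix 6 | Under 7.2.1 |
|---|---|---|
| Recorded as an adverse event | Yes | Yes |
| Grade | 3 | 3 |
| Relationship | Investigator's choice; Possibly Related is open | Unrelated |
| Count toward the 7.5 Grade 3 or 4 criterion | Up to 2, which meets it | 0 |

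The zero does not depend on the number of participants affected.

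**5. Grade 2.** The 7.5 criterion counts only Grades 3 and 4. A non-serious Grade 2 rate adds nothing to it with or without 7.2.1. The default changes only its entry in the relationship column.

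**6. Illustration.** Let p be the true proportion of participants with isolated Grade 3 tachypnea. No value of p is in the documents; those below are assumptions. With X binomial(n, p),

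P(X ≥ 2) = 1 − (1 − p)^n − n·p·(1 − p)^(n−1).

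For n = 20 and p = 0.05: 1 − 0.358 − 0.377 = 0.264 (from unrounded terms). For p = 0.10: 1 − 0.122 − 0.270 = 0.608.

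| Assumed p | One group, n = 20 | Both groups, n = 40 |
|---|---|---|
| 1% | 0.017 | 0.061 |
| 2% | 0.060 | 0.190 |
| 5% | 0.264 | 0.601 |
| 10% | 0.608 | 0.920 |
| 20% | 0.931 | 0.999 |

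These are probabilities of two or more cases. They would be pause probabilities only if every case were judged related when assessed individually. Under 7.2.1, with no evidence of pathology in any case, the contribution to the pause criterion is 0 in every row. If half of all Grade 3 cases came with pathology and were called related, the effective rate would be p/2: in one group of 20, 0.088 at p = 5% and 0.264 at p = 10%.

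**The case against.** The strongest defense is that 7.2.1 is a specific, explained and rebuttable exception to a general rule. The general rule is not absolute elsewhere either: Section 7.2 records solicited events without attribution and handles Ebola virus disease on its own form. This has some force, but tachypnea is not among the symptoms listed on the diary card, and the exception as worded goes further than its explanation.

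Safeguards that do not depend on attribution also stand. Grade 2 and 3 events through Day 28 are recorded, and they are tabulated by severity. The primary endpoint is the occurrence of adverse events, not of related ones. The Protocol Safety Review Team reviews all adverse events and sees aggregate data weekly during the vaccination period. Section 7.6.4 sends unexpected events above moderate severity to the ethics board and the national regulator within 7 days whatever their relationship. The DoD Research Monitor can stop the study. Grade 4 is intubation, which would be expected to come with pathology.

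Four stronger readings are tempting, and the documents do not support them:

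- A reader might infer that the rationale covers only rates near 20. The text says 20 or above; the fair criticism is that it is open-ended and unsupported for rates well above that.
- A reader might infer that the default takes Grade 2 events out of the pause rule. They were never in it.
- A reader might infer that these events would go unseen. They would be seen; what they could not do is meet the prespecified criterion.
- A reader might take 26% or 61% as the chance of a missed pause. Both rest on assumed rates and count cases, not cases that would be judged related.

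**Conclusion.** The point holds in a limited form. Section 7.2.1 sets an attribution default with no limit by grade or baseline, which its rationale does not support for Grade 3 rates or for rises above baseline, and which departs from Sections 7.1 and 7.2 and Appendix 6. For isolated Grade 3 tachypnea without evidence of pathology, the contribution to the Section 7.5 criterion is exactly zero at any frequency. That follows from the text alone. For Grade 2 the effect is confined to the relationship column.

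The practical size is unknown, because the documents give no rate for such events and no indication of how often investigators would judge them related. With review of all adverse events in place, this is an inconsistency worth correcting. It does not show that safety monitoring fails.

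**What to change.** Reconcile 7.2.1 with Sections 7.1 and 7.2 and Appendix 6 by rewriting the attribution clause along these lines:

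- A respiratory rate recorded as an adverse event that is Grade 3 or above, or that is an increase from the participant's baseline, receives an individual causality assessment by the investigator. It uses the Appendix 6 categories and takes local norms and altitude into account as footnote 6 already directs. Baseline is the pre-injection Day 0 evaluation, as Section 5.2.2 defines it.
- For recorded rates below Grade 3 that are not above baseline, the unrelated default may remain, still open to rebuttal by evidence of pathology.

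Restricting the default to Grade 1 values not above baseline would leave it nothing to act on, since 7.2.1 already keeps those values out of the adverse event record. The wording above keeps it for the case that the rationale does address: a participant in the Grade 2 range both before and after injection.

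The grades, the recording rule and the pause threshold are unchanged, and investigators remain free to judge any such event unrelated. The cost is a one-sentence revision and a few additional causality assessments.

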7.3 Protocol Safety Review Team

The PSRT will review all AEs (including reportable AEs) on a regular and expedited basis as needed. In addition, the PSRT will review aggregate safety data reports on a weekly basis until 4 weeks after all participants have completed the vaccination, then the safety reviews will occur monthly. The PSRT will review SAEs that potentially meet study pause criteria on an expedited basis and will decide if the study should be paused for participant safety purposes. This team includes the following: PI or designee, Associate Investigators, Protocol Consultants, DoD Research Monitor, sponsor IND Medical Officer or designee, and other VRC Representatives. Additional participants could include study personnel and senior clinical research nursing staff. A quorum is established with the PI or designee, one AI or designee, one MHRP protocol consultant or their designee, and IND Medical Officer or their designee. If the DoD Research

Monitor is not available for the PSRT call, they must provide input by email and then be immediately emailed the outcome of the PSRT discussion.

In addition to the regular and expedited meetings, the PSRT will conduct the following three interim safety data reviews to assess whether or not the safety data meet criteria for moving on to the next stage of the study.

Review for Continuation of 1 x 10¹⁰ PU Dose of VRC-EBOAD086-00-VP: No more than 1 participant per day will be enrolled into the group for the first 3 participants. When the first 3 participants who have received the 1 x 10¹⁰ PU dose have completed post vaccination follow up through at least the “Study Day 7” visit, an interim safety data review will be conducted by the PSRT. Enrollment of the remaining 17 participants in the group may proceed if the PSRT assesses the data as safe to continue.

Review for Dose Escalation to 1 x 10¹¹ PU Dose of VRC-EBOAD086-00-VP: When the last participant who has received the 1 x 10¹⁰ PU dose has completed post vaccination follow up through at least the “Study Day 7” visit, an interim safety data review will be conducted by the PSRT. If the safety data support proceeding to the 1 x 10¹¹ dose, then enrollment of Group 2 will begin.

Review for Continuation of 1 x 10¹¹ PU Dose of VRC-EBOAD08600-VP: No more than 1 participant per day will be enrolled into the group for the first 3 participants. When the first 3 participants who have received the 1 x 10¹¹ PU dose have completed post vaccination follow up through at least the “Study Day 7” visit, an interim safety data review will be conducted by the PSRT. Enrollment of the remaining 17 participants in the group may proceed if the PSRT assesses the data as safe to continue.

After each of these interim safety reviews, the IRB, NDA and VRC will be provided with documentation of the safety review and notification of the plan.

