It is anticipated that about 100 volunteers will be screened in order to enroll a total of 40 participants. The 40 participants will be evenly split, with 20 in each of the two dosage groups for cAd3-EBO S. The dose escalation plan includes daily review of any new safety data by a study clinician, regular review of safety data by the protocol team and a staged enrollment plan with required interim safety reviews. The study will begin with enrollment of 3 participants into Group 1 at a rate of 1 participant per day. After at least 7 days of follow-up for the first 3 vaccinated participants, an interim safety review will occur before enrollment of additional participants into the group. If no safety issues are identified, an additional 17 participants will be enrolled to complete Group 1. When there is a minimum of seven days of follow-up safety data from the last enrolled participant in Group 1, an interim safety review will occur. Once no safety issues are identified, enrollment of participants into the next dose level (Group 2) will begin with the enrollment of 3 participants at a rate of 1 participant per day. After at least 7 days of follow-up for the first 3 vaccinated participants in Group 2, an interim safety review will occur before the enrollment of additional participants into Group 2. If no safety issues are identified, an additional 17 participants will be enrolled to complete Group 2.

Product Description

VRC-EBOADC086-00-VP (cAd3-EBO S) is composed of a cAd3 vector that expresses Ebola Sudan WT GP. It is formulated at 1×10^{11} PU/mL.

VRC-DILADC065-00-VP (diluent) is the formulation buffer used for vaccine production and will be used when needed to prepare the 1×10^{10} PU/mL dose of cAd3-EBO S.

Participants

Healthy adults in the Kampala area aged 18-50 years will be enrolled.

Study Duration

Participants will be evaluated at 9 clinic visits over 48 weeks.

Study Objectives

Primary Objectives

- To evaluate the safety and tolerability of VRC-EBOADC086-00-VP when administered IM at a dose of 1×10^{10} particle units (PU) to healthy adults;
- To evaluate the safety and tolerability of VRC-EBOADC086-00-VP when administered IM at a dose of 1×10^{11} PU to healthy adults.

Secondary Objectives

- To evaluate the antibody response to the GP insert and cAd3 vector in VRC-EBOADC086-00-VP at 4 weeks after vaccination as assessed by GP ELISA and vector-specific neutralization assays, respectively.

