4.0 STUDY DESIGN AND POPULATION

This is a Phase I open-label, dose-escalation clinical trial to evaluate the safety, tolerability and immunogenicity of a recombinant vector for the Sudan strain of the Ebola virus. This study will be conducted at the MUWRP in Kampala, Uganda.

A total of 40 healthy adults, 20 in each dosage group, will receive a single vaccine injection of cAd3-EBO S at 1×10^{11} PU/mL or 1×10^{10} PU/mL. The study will begin with enrollment of 3 participants into Group 1. After at least 7 days of follow-up for the first 3 vaccinated participants, an interim safety review will occur before enrollment of additional participants into the group. If no safety issues are identified, an additional 17 participants will be enrolled to complete Group 1. When there is a minimum of seven days of follow-up safety data from the last enrolled participant in Group 1, an interim safety review will occur. Once no safety issues are identified, enrollment of participants into the next dose level will begin with the enrollment of 3 participants. After at least 7 days of follow-up for the first 3 vaccinated participants in Group 2, an interim safety review will occur before enrollment of additional participants into Group 2. If no safety issues are identified, an additional 17 participants will be enrolled to complete Group 2. For the first 3 participants in each group, only one participant per day will be enrolled. The study groups and vaccination schema is shown in Table 1.

Study agent administration will be on Day 0. The study includes daily review of any new safety data by a study clinician and weekly review of safety data by the Protocol Safety Review Team (PSRT). The staged enrollment plan and plan for interim safety reviews (Section 7.3) applies to both Group 1 and Group 2. The interim safety reviews will be conducted by the PSRT.

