7.2 Adverse Event Grading and Recording

Recording of all AEs will occur during the period from study agent administration through 28 days after study agent administration. Solicited AEs will be recorded in the study database for 7 days after injection without the collection of attribute assessments. All unsolicited AEs and SAEs that occur during the period from study agent administration through 28 days after study agent administration will be recorded in the study database. After study day 28, only SAEs and new chronic medical conditions that require ongoing medical management will be recorded as AEs in the study database. Because this is an Ebola vaccine study, in the unlikely circumstance of Ebola virus disease (EVD) diagnosis in a study participant at any time throughout the study, this will be recorded on an “EVD CRF”, rather than an AE form, without requiring an investigator attribution (“relatedness to study agent”) or severity grade.

The FDA Guidance for Industry (September 2007): “Toxicity Grading Scale for Healthy Adult and Adolescent Volunteers Enrolled in Preventive Vaccine Clinical Trials” was adapted for the

severity grading of adverse events in this protocol. The FDA Guidance of Industry on toxicity grading scale is modified for criteria on absolute neutrophil counts and other parameters as described in Appendix 6, which also includes the definitions for severity grading parameters that do not have specific guidelines in the table. Due to the absence of specific grading criteria for arthralgias on the FDA toxicity grading scale, the “DAIDS AE Grading Table Corrected” (Version 2.1-July 2017) (Appendix 7) will be used to grade arthralgia AEs.

The clinical investigators will monitor and analyze study data including all AE and lab data as they become available and will make determinations regarding the severity of the adverse experiences and their relation to study product. AE CRFs will be completed by the research staff on a daily basis as the data become available from the clinic or laboratory. AEs are also subjected to analysis to identify those that may invoke study pause rules. To ensure that all AEs are captured in a timely manner, AE CRFs will be entered into the database within 24 hours. All other CRFs will be entered into the database within 3 business days. All CRFs will be subjected to analysis to identify AEs that may invoke study pause rules.

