APPENDIX 1: SCHEDULE OF EVALUATIONS

RV 508 Schedule of Evaluations												
Visit	01	02	02A	02B	02C	02D	03	04	05	06	07	
Week of Study	-8 to 0	W 0	W 1	W 1	W 1	W 2	W 4	W 8	W 16	W 24	W 48	
Day of Study	-56 to 0	D 0	D 1	D 3	D 7	D 14	D 28	D 56	D 112	D 168	D 336	
Clinical Evaluations	Screening ¹	Enrollment										
Informed Consent, Assessment of Understanding	X											
Physical exam and weight at screen; Vital signs, targeted exam at other visits	X	X		X	X	X	X	X	X	X	X	
Medical history for eligibility at screen; interim history other visits	X	X		X	X	X	X	X	X	X	X	
Study Vaccination ²		X										
Begin/Review 7-Day Diary Card ⁶		X		X	X							
Telephone contact; clinic visit if indicated			X									
Counseling on pregnancy prevention		X				X	X	X	X			
CBC w/total lymphocyte count	3	3		3	3	3	3	3		3		
Pregnancy test: urine (or serum) ³	X	X					X			X		
Creatinine and ALT	4	4		4	4	4	4	4				
HIV ⁵ and RPR	6											
Research Immunology												
Serum storage for antibody assays	12	12		12	12	12	12	12	12	12	12	
Pre-Existing Vector Immunity testing	X											
PBMC and plasma for storage	8.5	68			59.5	42.5	59.5	42.5	59.5	76.5	76.5	
Intracellular RNA		3		6	6							
HLA type ⁴									17			
Daily Volume (mL)	33.5	90	0	25	77.5	61.5	78.5	61.5	88.5	91.5	88.5	
Max. Cumulative Volume (mL)	33.5	123.5	123.5	148.5	226	287.5	366	427.5	516	607.5	696	

Visit windows: 02A (+1 day); 02B (+2 days); 02C (+3 days); Visit 02D (± 3 days); Visits 03 and 04 (± 7 days); Visits 05, 06 and 07 (± 14 days).

¹ Most screening evaluations must be no more than 56 days prior to Day 0 to be used for eligibility (pregnancy test from Day 0 must be used for eligibility). If clinical assessment on Day 0 suggests significant changes may have occurred since screening, then physical examination & laboratory studies done on Day 0 are used for eligibility.

Day 0 = day of enrollment and vaccine injection. Day 0 evaluations prior to first injection are the baseline for assessing adverse events subsequently.

² Complete post vaccination vitals and injection site assessment after the study injection (target to complete this within the interval 30 to 45 minutes post-vaccination). Subjects must remain in the clinic for at least 30 to 60 minutes after injection.

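### The dose-escalation review can open on the last-enrolled participant's Day 7 visit while other Group 1 participants' Day 7 visits are still outstanding and in window

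*Combined protocol and SAP*

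**What the plan says.** Section 7.3 (Protocol Safety Review Team, PSRT) sets three interim safety reviews.

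- **First-three reviews, one in each group.** These are held "When the first 3 participants who have received the" dose in question have completed follow-up through at least the Day 7 visit. All three participants under review must have been seen.
- **Escalation review.** This is held "When the last participant who has received the" 1 × 10^10 PU dose has completed the same follow-up. One person's visit is the trigger.

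The Schema and Section 4.0 state the escalation trigger as "When there is a minimum of seven days of follow-up safety data from the last enrolled participant in Group 1". That wording ties it to enrolment order.

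Two other provisions matter. Section 4.0 limits pacing to the start of each group: "For the first 3 participants in each group, only one participant per day will be enrolled". No daily cap is stated for the remaining 17. Appendix 1 gives the visit windows as "02B (+2 days); 02C (+3 days"), so the Day 3 visit may fall on Days 3 to 5 and the Day 7 visit (02C) on Days 7 to 10, with no early side.

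**The concern.** Enrolment order does not fix visit order when the visit has a three-day late window. The last-enrolled participant may attend promptly on Day 7 while someone vaccinated the same day, or a day or two earlier, attends later and still in window. As written, the review could then proceed without that person's Visit 02C: CBC, creatinine and ALT, vital signs, interim history and diary review.

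This is the only gate between the two dose levels, and the step is ten-fold. Its entry condition should cover all 20 participants under review, as the first-three reviews cover all of theirs. The text also does not say what happens if another Group 1 participant misses the visit altogether.

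**Working it through.** **Inputs from the documents.** Visit 02C window: Day 7 to Day 10 (Appendix 1; Appendix 3 agrees). Group 1 size: 20. Pacing: one per day for the first three only (Section 4.0). Trigger: last-enrolled participant (Schema, Sections 4.0 and 7.3).

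**Who can be outstanding.** Count days from the last Group 1 vaccination. Someone vaccinated *k* days earlier and seen on their own Day *V* attends on the last participant's Day *V* − *k*. If the last participant is seen on Day *L* and the review is *d* days later, the visit is outstanding when *V* − *k* > *L* + *d*. The latest in-window *V* is 10, so this needs *k* < 10 − *L* − *d*.

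- *L* = 7, *d* = 0: *k* = 0, 1 or 2
- *L* = 8, *d* = 0: *k* = 0 or 1
- *L* = 9, *d* = 0: *k* = 0
- *L* = 10, or *d* = 3 with any *L*: nobody

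**How likely.** The plan gives no enrolment rate, attendance pattern or review timing, so I assumed ranges: steady enrolment of 1, 2 or 3 per day, and independent Day 7/8/9/10 attendance of 90/6/3/1%, 70/15/10/5% or 25% each. The numbers of other participants at *k* = 0, 1, 2 are then 0, 1, 1 (1/day), 1, 2, 2 (2/day) and 2, 3, 3 (3/day).

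P(at least one outstanding) = Σ over *L* of p(*L*) × [1 − Π over *k* of (1 − P(*V* > *L* + *d* + *k*))^n_k]

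Worked case: 2/day, 70/15/10/5%, *d* = 1.

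- *L* = 7: 1 − 0.85 × 0.95² = 0.2329
- *L* = 8: 0.05
- *L* = 9 or 10: 0
- Total: 0.70 × 0.2329 + 0.15 × 0.05 = 0.171

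Results, with the three attendance patterns in order:

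| Review lag *d* (days) | 1/day | 2/day | 3/day |
|---|---|---|---|
| 0 | 4.5 / 14.2 / 21.9% | 17.2 / 42.0 / 48.3% | 28.1 / 58.6 / 58.2% |
| 1 | 0.9 / 3.5 / 6.25% | 5.4 / 17.1 / 24.2% | 9.6 / 28.1 / 33.3% |
| 2 | 0 | 0.9 / 3.5 / 6.25% | 1.8 / 6.8 / 10.9% |
| 3 | 0 | 0 | 0 |

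The expected number outstanding at *d* = 1 is 0.01–0.06, 0.05–0.31 and 0.10–0.56 at 1, 2 and 3 per day.

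**In-window maxima** (last participant seen on Day 7, all others on their Day 10), at 1, 2 and 3 per day: 2, 5 or 8 of 20 at *d* = 0; 1, 3 or 5 at *d* = 1; 0, 1 or 2 at *d* = 2; none at *d* = 3.

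**Precision.** With no events among 20, the exact 95% upper limit is 1 − 0.025^(1/20) = 16.8%, which agrees with Table 4. At the *d* = 1 maxima, Day 7 data would exist for 19, 17 or 15 participants, and the limit becomes 17.6%, 19.5% or 21.8%.

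**Exposure at the higher dose.** The latest outstanding in-window visit is due on the last participant's Day 10. Group 2 starts at no more than one per day. If the review falls on that participant's Day 7, 8, 9 or 10 and dosing begins the same day, at most 3, 2, 1 or 0 people receive 1 × 10^11 PU before that visit is due.

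**The case against.** The strongest reply is that the last participant having completed follow-up is ordinary shorthand for the whole group having done so. The Schema and Section 4.0 also set an elapsed-time floor, which anyone enrolled earlier necessarily meets. The second part is true: everyone has at least seven elapsed days. But Section 7.3 asks for a completed visit, and the words about enrolment order in the other two places undercut the shorthand reading. If shorthand was meant, the text should say so.

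The second reply is practical. The last participant's laboratory results must come back. On data entry, Section 7.2 says "All other CRFs will be entered into the database within 3 business days" (adverse event forms are due within 24 hours). Four parties must also meet: "A quorum is established with the PI or designee, one AI or designee", plus an MHRP protocol consultant and the IND Medical Officer or their designees. A same-day review is therefore the least plausible case, and the *d* = 0 row is an upper end. This stands. But the plan sets no minimum lag, and the chance reaches zero at every rate only at three days.

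Third, the missing data are not where most risk is expected. Sections 1.2.2 and 10.1.1 place systemic reactogenicity on the day of vaccination or the next day. The Day 1 contact and the Day 3 clinic and laboratory visit cover that period for anyone on schedule. Clinicians review new safety data daily, participants may call or attend at any time, and the pause rules in Section 7.5 apply throughout. The trigger is a minimum, so the PSRT may wait, and Group 2 opens only on its judgement ("If the safety data support proceeding to the" higher dose). A further review follows the first three at that dose. All of this limits the harm. It does not supply a Day 7 laboratory result that has not been drawn, and a pause rule cannot act on an abnormality nobody has seen.

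Finally, requiring Visit 02C does not guarantee a collected diary, because Appendix 1 allows collection up to Visit 02D. That is correct and limits what the fix achieves.

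**Conclusion.** The concern holds, at minor severity. The escalation trigger rests on one participant's visit, and the visit window together with uncapped enrolment after the first three lets others be unseen and in window. The calendar result follows from the documents alone. The probabilities depend on the assumed enrolment rate, attendance and review lag: at a one-day lag, about 1–6% at one enrolment per day and 10–33% at three per day, with fewer than one participant expected to be outstanding in every case. What may be missing is one late set of safety assessments for a few people. Neither the endpoints nor the planned analyses are affected.

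**What to change.** In Section 7.3, Section 4.0 and the Schema, replace the escalation trigger with:

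> The escalation review is held once every vaccinated Group 1 participant has completed Visit 02C, or is documented as having missed it (own Day 10 passed) or as withdrawn, with all available Visit 02C laboratory results included.

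This brings the gate up to the all-participants standard of the first-three reviews and adds a missed-visit rule, which those reviews lack. Escalation with some Day 7 data missing remains possible, but the gap would be documented and known to the PSRT.

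The cost is one sentence in three places and a possible wait of up to about three days after the last participant's Day 7. A visit made after Day 10 would not hold up the review; its data would reach the PSRT through the weekly safety reports. Dose levels, group sizes and length of follow-up do not change.
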